6.6 BASELINE SURVEY WITH MAPPED SOCIAL NETWORKS AND PROMOTERS SOCIAL NETWORKS

Based on men who have agreed to be in the study and were mapped to social networks and randomized, we will conduct a baseline survey with all network members and their central promoters. This baseline survey will include socio-demographic, health and sexual behaviors, including HIV testing history and will serve as the baseline for a number of measures prior to the study implementation.

The baseline survey is included as an attachment to this protocol.

6.7 FOLLOW UP SURVEY

Following randomization, study enrollment and participation in the baseline survey, at about 3 months we will conduct a follow-up survey to assess the primary outcome of HIV testing. Following this window, we will conduct follow up interviews with the baseline survey cohort (those who were randomized to a network and participated in the baseline survey) as well as additional new participants who received a self-test from central network promoters.

Three versions of the 3-month follow up survey is included as an attachment to this protocol.

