Follow up surveys will be conducted with study participants at 3 months. Please note that at this stage of the data collection, there will be three possible study participants groups for which we will provide individualized surveys, (1) those who were mapped during the social network mapping exercise and identified as a part of the network where the central promoter was randomized to control or intervention, (2) those who were not mapped or named during the baseline social network mapping exercise but received an HIVST with an incentive voucher (intervention) or referral voucher (control) from a central promoter, and (3) central promoters themselves. These surveys will assess self-reported HIV testing among study participants, whether they sought confirmatory testing, whether they linked to ART or PrEP, interactions they had with study promoters, as well as assess health behaviors. We will have three versions of the follow up survey which are attached to this protocol.

8.7 BIOSPECIMEN COLLECTION AND CLINICAL DATA TO ASSESS CONFIRMATORY TESTING, LINKAGE TO ART AND PREP, AND LONG TERM OUTCOMES

*Up to n=1500 participants**

* We do not know aprior the rate of care or prevention uptake so the total numbers are tentative.

Visit 2 (for 6 months) for new participants (those not mapped in the baseline but received self-tests with incentive vouchers (intervention) or referral vouchers (control) from promoters and then linked to care or prevention

Visit 4 (for 6 months) for baseline mapped and surveyed participants who received self-tests with incentive vouchers (intervention) or referral vouchers (control) from promoters and then linked to care or prevention

Visit 5 (for 6 months) for promoters who will have participated in the social network survey, baseline survey, and promoter trainings (visits 1 2 and 3, respectively) and then linked to care or prevention

We will obtain informed consent in clinics, from all of the study participants who opt to visit a study clinic for confirmatory testing, for the release of medical record data. The clinical data abstraction and follow

up bio-specimen collection will take place for two cohorts (1) those who HIV test, link to care and are enrolled in care and taking ARVs, and (2) those who HIV test, are HIV-negative, screened and eligible for and start PrEP. The chart abstraction data focused on 6-month outcomes will be collected retrospectively through the end of year 4, June 2023.

HIV-positive study participants

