1.3.2 ANALYSIS OF THE PRIMARY ENDPOINT(S)

Primary Outcome: The primary outcome will be self-reported HIV testing in the past 3 months by participants, as measured in the 3-month follow-up surveys.

Primary Predictor: Cluster (social network) Randomized Arm (intent-to-treat), Intervention or Control.

Analytic Plan: For the test of the intervention effect on the primary outcome of self-reported HIV testing in past 3 months, we will utilize a cluster adjusted Pearson's Chi-square test comparing the proportion of subjects' HIV testing in the intervention versus the control arm. In secondary analysis, we will utilize multilevel mixed-effects logistic regression with cluster-adjusted standard errors and a binary outcome of reported HIV testing or not (including cluster as one of the levels with random effects allowed). We will

investigate factors that influence the probability of success of HIV testing, including characteristics of clusters (the close social networks' size and composition, metrics of connectedness, mean cluster self-testing rate), characteristics of the cluster's promoter (age, marital, HIV, ART, PrEP status, measures of the promoter's ties to close-social-network cluster members), and individual level characteristics (demographics, SES, prior HIV testing, duration in boat crew, self-reported HIV risk).

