## 20) Analysis populations:

Definition of analysis populations, e.g. intention to treat, per protocol, complete case, safety, and other.

- a. Intent to treat: Those who were randomized to intervention and control groups (regardless of whether or not they received the kit from their "promotor")
- b. Per protocol: Those who were members of a cluster that was randomized to the intervention and meet specific criteria per aim will be part of the per-protocol analysis. For Aim 1, it will be those individuals in the intervention arm who received an HIV self-testing kit. For Aims 2 and 3, it will be those individuals in the intervention arm who received a kit and attended a clinic visit.
- c. Complete case— We will not conduct complete case analyses as we will attempt to use all available data from all participants (see section 29: Missing Data).

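### Protocol and SAP do not agree on whether men who were never mapped or randomised, enrolled after allocation because a promoter reached them, count in the primary outcomes

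*Protocol*

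**What the plan says.** **Who is surveyed.** Protocol 6.7 gives the purpose of the 3-month contact: "we will conduct a follow-up survey to assess the primary outcome of HIV testing". It then lists the baseline survey cohort "as well as additional new participants who received a self-test from central network promoters". Protocol 8.6 names three participant groups for this survey. One is men not mapped or named at baseline who "received an HIVST with an incentive voucher (intervention) or referral voucher (control) from a central promoter". Consent item 6 in Protocol 4.1.2 covers the same men, in both arms. Protocol 8.7 schedules 6-month visits for those among them who link to care or prevention, and item 6 asks for release of their medical records.

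**Who is analysed.** Protocol 1.3.2 states: "The primary outcome will be self-reported HIV testing in the past 3 months by participants, as measured in the 3-month follow-up surveys". The predictor on the next line is "Cluster (social network) Randomized Arm (intent-to-treat), Intervention or Control". SAP 20 defines the intent-to-treat set as "Those who were randomized to intervention and control groups", whether or not they received a kit. SAP 26 again speaks only of study participants. The SAP cites Protocol Version 4.0, the supplied protocol is Version 11.0, and the SAP does not mention the additional men.

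**The concern.** The documents conflict in two ways.

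- **Denominator.** In the protocol's own vocabulary the unmapped men are participants in the 3-month surveys, so they fall within the literal wording of the primary outcome. The SAP's set, and the intent-to-treat label in 1.3.2, leave them out. The same gap runs into linkage and the 6-month composite, because 8.7 collects those data on them.
- **Entry rule.** 6.7 admits kit recipients only, which in practice means the intervention arm. 8.6, 8.7 and 4.1.2 also admit men given a referral voucher by a control promoter.

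An unmapped man was not allocated to anything. He enters after randomisation because a promoter handed him a kit or voucher, so his arm is set by exposure, and he has no pre-intervention survey. SAP 28 counts missing primary outcomes as failure. Randomised men lost to follow-up therefore count as non-testers, whereas unmapped men are identified at follow-up and largely escape that rule. Two analysts could follow these documents to different primary results, and the choice could be made after the data are seen.

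**Working it through.** **Inputs from the documents.** Protocol 1.2, Aim 1: control testing 38%, intervention 52%, ICC 0.15, 70 clusters per arm of average size 7, type I error 5%. SAP 16: two-sided tests. Protocol 8.4 and 8.6: up to 1000 men at baseline and up to 1500 at 3 months. Protocol 8.5: one kit for each promoter plus up to 8 for his network members.

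**Assumptions.** The documents give neither the number of unmapped men nor their testing rate.
- Number k: if the promoter is one of the 7, there are 70 × 6 = 420 kits for other men. Diverting 10%, 20% or 30% gives k = 42, 84 or 126.
- Testing rate q among kit recipients: 60%, 80% and 91%. The 91%, and the 52% used below for voucher recipients, are borrowed from the trial among pregnant and postpartum women described in Protocol 6.9, which is a different population.

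**The plan's own figure.** Design effect = 1 + (7 − 1) × 0.15 = 1.90. Effective size per arm = 490 / 1.90 = 257.9. Two-sided power for 38% versus 52% is 89%, consistent with the stated 80% or greater. The odds ratio is (0.52/0.48)/(0.38/0.62) = 1.77, stated as 1.8.

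**Randomised men only, no effect.** 38% versus 38%: rejection 5.0% (5.5% in a beta-binomial simulation of 20,000 runs).

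**Additions in the intervention arm only (the 6.7 wording), no effect.** Intervention rate = (490 × 0.38 + kq)/(490 + k). For k = 84 and q = 80%: (186.2 + 67.2)/574 = 44.1%, a false gain of 6.1 points. Rejection uses a two-sided 5% z test with 490 per arm and design effect 1.9. In this case the standard error is about 0.043, and Φ((0.0615 − 1.96 × 0.0433)/0.0432) = 29%.

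| Added men | q = 60% | q = 80% | q = 91% |
|---|---|---|---|
| 42 | +1.7 points, 7% | +3.3, 12% | +4.2, 16% |
| 84 | +3.2, 12% | +6.1, 29% | +7.8, 43% |
| 126 | +4.5, 18% | +8.6, 51% | +10.8, 70% |

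Letting the intervention arm and its design effect grow with k moves these rejection figures by no more than about 2 percentage points. Simulation of neighbouring cases (70 and 140 added men at 90%) gave 37% and 85%, against 33% and 78% by formula, so the formula is if anything slightly low.

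**Additions in both arms (the 8.6 wording), no effect.**
- 84 per arm, 80% versus 52%: 44.1% versus (186.2 + 43.7)/574 = 40.0%. Net +4.1 points, rejection 16%.
- 84 per arm, 80% versus 60%: 44.1% versus 41.2%. Net +2.9 points, rejection 10%.
- 84 per arm, 80% in both: net 0, rejection 5%.
- 70 kit recipients at 90% and 210 voucher recipients at 75%: (186.2 + 63)/560 = 44.5% versus (186.2 + 157.5)/700 = 49.1%. Net −4.6 points.

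**The case against.** **Pooling is not stated.** A reader might infer that the protocol plans to count the unmapped men in the arm comparison. The documents do not support that. Protocol 6.7, 8.6, 8.7 and 4.1.2 say whom to survey, consent and abstract, which is data collection. The predictor in 1.3.2 is labelled intent-to-treat. The synopsis, 1.1 and 1.3.3, and SAP 9, frame the comparison by men in assigned networks. This objection stands, and it limits the defect to an unsettled denominator. It does not close the gap: no sentence excludes these men. Nor does their lack of a network rule out pooling, since Protocol 9.2 puts cluster IDs on kits and vouchers, so an unmapped man could be attributed to a promoter's cluster.

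**Bias need not favour the intervention.** A reader might also infer that testing in the intervention arm is necessarily inflated against control. That holds only for the 6.7 wording, and only if recipients test at above 38%. The fuller procedures add control men too, so size and sign depend on numbers and rates the documents do not give.

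**The null is demanding.** It supposes that unmapped recipients test at 60% to 91% while mapped men, who receive the other 294 to 378 kits, stay at 38%. If mapped men used those kits at 80%, their testing would be about 63% to 70% and there would be no null. This is fair: the rejection figures describe strongly selected recipients. The distortion does not need a null, however. With mapped testing at the planned 52%, 84 added men at 80% give (254.8 + 67.2)/574 = 56.1%, a 4.1-point overstatement.

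**Safeguards exist.** Promoters are told to keep to their own networks, the unmapped men have their own survey version, and 9.1 and 9.2 already plan to measure off-network distribution. These make the men identifiable and may keep their number small, but they do not define the analysis set. The 500-man gap between the survey ceilings is a difference of two maxima across both arms, not a forecast. Part of the mismatch is version lag in the SAP, which explains the gap without resolving it.

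**Conclusion.** The concern holds as a conflict over who is counted in the primary outcomes, together with an inconsistent entry rule for the unmapped men. It does not show that the planned comparison is already broken. If only intervention recipients were counted, 42 to 126 men would give a false gain of about 2 to 11 points and rejection of about 7% to 70% instead of 5%. If recipients in both arms were counted, the bias is a net figure: about +4 points and 16% rejection for 84 men per arm at 80% versus 52%, nil under symmetry, and reversed if control adds enough men. All of these rest on assumed numbers and testing rates, and on a null with 490 mapped men per arm and ICC 0.15. It should be settled before analysis, because it fixes the denominator of the first primary outcome and bears equally on linkage and the 6-month composite.

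**What to change.** - In Protocol 1.3.2, 1.3.3 and 8.6 and SAP 20 and 26, state that every Aim 1, 2 and 3 arm comparison includes only men mapped to a network before that network was randomised.
- State that unmapped recipients are reported separately, by arm of the promoter who reached them, as part of the fidelity and spillover description in Protocol 9.1 and 9.2.
- Reconcile the entry rule in Protocol 6.7 with those in 8.6, 8.7 and 4.1.2.
- Update the SAP to the current protocol version so that it names this group.

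The cost is a few sentences. No randomised data are lost, and the unmapped men's surveys keep their use for describing reach and contamination.

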6.8 QUALITATIVE STUDIES

6.8.1.1 OVERVIEW

Across all aims, assess pathways of intervention action using qualitative and mixed methods. Identify mechanisms of action, and barriers and facilitators of the social network and incentives intervention implementation, using qualitative and mixed methods (quantitative and qualitative) assessments embedded in Aims 1, 2 and 3 (at baseline, and at follow-up time points corresponding to quantitative measurements in all aims).

Analytic Approach: Mixed-methods approach of qualitative analysis of key informant interviews and focus groups combined with quantitative process and fidelity measures and trial outcome data.

We will use a rigorous two-phased analysis approach, beginning with: 1) qualitative analysis of in-depth and key informant interview and FGD data, using a grounded theoretical approach that involves iterative inductive coding of empirical data (transcripts); followed by a 2) mixed-methods analysis of qualitative data grouped by categories defined using social network survey data, process and fidelity measures, and trial outcome data. This will involve analyzing qualitative data collected within categorized groups of participants including (but not limited to) testers vs. non-testers, linkers vs. non-linkers to ART and PrEP, virally suppressed vs. detectable VL, and PrEP adherent vs. non-adherent. This approach will allow us to identify emergent themes within groupings and to rigorously assess conceptual alignment or differences across groupings, with attention to evidence of contradictory findings and deviant cases in the data. Primary Research Questions: Investigations will be focused on three domains (Table 2): 1) mechanisms of action of the intervention that result in success or failure in Aim 1 (HIVST usage), Aim 2 (linkage to ART or PrEP), and Aim 3 (suppressed or unsuppressed or detectable TFV levels in urine), 2) key issues impacting the effectiveness of individual components of the intervention, and 3) barriers and facilitators of implementation of the intervention.

Table 3. Qualitative and Mixed Methods (quantitative and qualitative) Research Domains and Topics by
Research Aim

Domain	Aim 1 Topics	Aim 2 Topics	Aim 3 Topics
Mechanisms of intervention action	 Attributions for decision to test Role of promoter: perceived influence Other barriers & facilitators to testing Attitudes & expectancies re: use of HIVST Perceived norms re: testing within close social network Vicarious efficacy re: HIV self- testing (seeing peers successfully use HIVST) 	 Attributions for decision to link Role of promoter: perceived influence Role of incentives Attitudes & expectancies re: ART & PrEP Perceived norms re: linkage to ART & PrEP within close social network Vicarious efficacy re: linkage (seeing peers successfully link to ART or PrEP) 	 Attributions for ongoing engagement in HIV care (ART) & prevention (PrEP) Role of promoter: perceived influence Role of incentives Perceived norms re: engagement in ART & PrEP within close social network Vicarious efficacy (seeing peers successfully engaged in ART or PrEP)
Factors impacting effectiveness of intervention components	 Knowledge of how to use self- tests (effectiveness of promoter training) Relationship factors (e.g. HIV status disclosure, HIV seroconcordant/ discordant status) Psychological factors (e.g. perceived risk, fear, fatalism, self-efficacy to test for HIV) 	 Knowledge of benefits of ART and PrEP (effectiveness of promoter training) Relationship factors (e.g. HIV status disclosure, partner support) Psychological factors (e.g. expectancies, fear, fatalism, self- efficacy to link) 	 Experiences with ART / PrEP (perceived emotional, physical benefits/costs) Effective management of side effects Relationship factors (e.g. relationship change, disclosure, partner support) Psychological factors (e.g. ART/PrEP fatigue, changes in risk, self-efficacy)
Barriers and facilitators of implementation	 Role of promoter: salience, trust towards promoter within network Promoters' self-perceptions & motivation 	 Individual mobility and distance to clinic Past and current experiences with providers / perceived quality of care 	 Individual mobility and distance to clinic Past and current experiences with providers / perceived quality of care

6.8.1.2 SAMPLING AND RECRUITMENT

Qualitative Study Populations: 1) In-depth interviews (IDIs). Sample up to 40 participants, selected to be equally balanced across study arms (i.e. 20 men per arm); 2) Key informant interviews (KIIs). Sample up to 15 promoters from the intervention, and 15 in the control arm. 3) Focus group discussion (FGD) groups.

1-2 focus groups per study arm, with 8-12 participants in each group. FGDs will include participants from all study sites, stratified by HIV status.

Sampling approach. We will use a qualitative sampling strategy drawing from grounded theory, in which sampling, data collection and analysis processes are iterative: we will use baseline data to define initial sampling categories (balance across study arms by age, fishing status (occupation) for selection of the first several participants in each category, and thereafter select additional participants according to new categories based upon emergent findings: sampling is completed when data are 'saturated', i.e. no emergent findings elicit a need for additional participants. Thresholds are defined for practical reasons of study schedule and budget. Recruitment will be iterative, using sample lists generated using data collected from the baseline BMU register review and baseline/follow up surveys, among participants who indicate during the informed consent process that they are willing to participate in qualitative research.

6.8.1.3 ANALYTIC APPROACH

Analytic Approach: We will use a rigorous two-phased analysis approach, beginning with: 1) qualitative analysis of in-depth interview and focus group discussion data, using a grounded theoretical approach that involves iterative inductive coding of empirical data (transcripts); followed by a 2) mixed-methods analysis of qualitative data grouped by categories defined using social network survey data, process and fidelity measures, and trial outcome data. This will involve analyzing qualitative data collected within categorized groups of participants including (but not limited to) testers vs. non-testers, linkers vs. non-linkers to ART and PrEP, virally suppressed vs. detectable VL, and PrEP adherent vs. non-adherent. This approach will allow us to identify emergent themes within groupings and to rigorously assess conceptual alignment or differences across groupings, with attention to evidence of contradictory findings and deviant cases in the data. The qualitative instruments for the IDIs, KIIs and FGDs described are included as attachments to this protocol. Future follow up qualitative tools may be submitted as amendments to the protocol.

6.9 JUSTIFICATION FOR INTERVENTION

Social network-based approaches show promise for generating positive social influence and accelerating health behavior change in men. The influence of social networks on health behaviors and outcomes is well established⁷⁸⁻⁸⁴ and it is known that social network characteristics can influence behavior through the circulation of ideas and social influence.⁸⁵ Network interventions are purposeful efforts to use networks to generate social influence, accelerate behavior change, and achieve positive health outcomes.⁸⁶⁻⁹¹ In SSA, prior research has shown the influence of social networks on HIV testing,⁹²⁻⁹⁴ partner concurrency,⁹⁵ and condom use.⁹⁶ Such an approach is further supported by research showing that behavioral and organizational change programs are most effective when implemented by members of the group undergoing the change, i.e., peers.^{97,98} We also now know that selecting influential nodes in a network (i.e. individuals who are highly connected) results in superior intervention effectiveness: selecting well-connected nodes, from a network perspective, are better than nodes chosen randomly, a finding demonstrated with simulations ^{99,100} and empirical examples.^{101,102} Thus, selecting highly socially connected men within social networks to act as 'promoters' may be overcome long-standing barriers to HIV testing and uptake of additional health services including HIVST.

Countries in SSA are scaling-up HIVST to close the testing gap in priority populations – evidence is needed on delivery approaches that maximize testing coverage. A growing number of countries, including Kenya, are scaling-up HIVST after the WHO's December 2016 guidelines called for large-scale implementation of HIVST.⁷⁵⁻⁷⁷ The feasibility of HIVST interventions was further enhanced by the Gates Foundation's 2017 decision to subsidize oral fluid-based HIV tests, bringing their price down to \$2/test. What countries are actively seeking are optimal distribution strategies for self-tests, to ensure that testing is increased among high-risk individuals not. Studies on secondary distribution of self-tests. Our pilot study on secondary distribution of self-tests enrolled HIV-negative pregnant women and FSW in Kisumu. Participants were shown how to use oral fluid-based self-tests and given 3-5 tests with easy-to-use instruction sheets. Overall, 90% of women reported their primary sexual partner used a self-test. Women reported high acceptability of HIVST among men and over 85% of men found self-tests easy to use. The proposed study builds on this work and targets men who are not partners of pregnant women and who may be reached more effectively through their peers. We followed the pilot study with an RCT that randomized pregnant & postpartum women to receive two self-tests or invitation cards for partners to seek clinic-based testing. Partner testing occurred for 91% of women in the intervention group and 52% of women in the control group (P<0.001). This finding was confirmed in another study in Uganda¹²³ and several programs in SSA are now this approach in antenatal clinics. This work underscores a high interest in HIVST among men and suggests feasibility of an intervention in which men offer self-tests to their peers. While distribution of self-tests by pregnant women has much promise, the approach may not reach all high-risk men, which motivates a study on men's social networks.

6.10END-OF-STUDY DEFINITION

A participant in the RCT is considered to have completed the study if he has completed at least the 6 month (-/+ 1 month) follow-up VL assessments if HIV-positive, and the 6 month (-/+ month) PrEP adherence assessment (if HIV- negative and eligible for and on PrEP).

